10.5. Pharmacokinetic Analysis

10.5.1. Ibrutinib

Ibrutinib and PCI-45227 bioanalytical data will be used in noncompartmental PK analysis. Plasma concentrations below the lowest quantifiable concentration will be treated as zero in the summary statistics. All subjects and samples excluded from the analysis will be clearly documented in the PK report.

Descriptive statistics will be used to summarize ibrutinib and PCI-45227 concentrations at each sampling time point and PK parameters of ibrutinib and PCI-45227 (including, but not limited to: C_{max} , T_{max} , AUC_{last} , and $t_{1/2}$) at each dosing interval.

Individual and mean plasma ibrutinib and PCI-45227 concentration time profiles will be plotted.

Ibrutinib data from this study may also be combined with data from other studies performed with ibrutinib in subjects with hematologic malignancies as part of a population-PK analysis using nonlinear mixed effects models. For the population-PK analysis, covariates that could potentially correlate with plasma PK parameters will be evaluated. The results of the population-PK analyses (if performed) will be presented in a separate report.

Steady-state ibrutinib PK data when administered alone in the lead in period will be compared to the data when administered in combination with venetoclax to explore the potential for a pharmacokinetic interaction between ibrutinib in combination use with venetoclax.

Ibrutinib model-derived exposure parameters (PK parameters) may be used to explore PK/PD correlation between the exposure of ibrutinib with relevant clinical [REDACTED] information to assess effectiveness and toxicity.

10.5.2. Venetoclax

Venetoclax bioanalytical data will be used in noncompartmental PK analysis. Plasma concentrations below the lowest quantifiable concentration will be treated as zero in the summary statistics. All subjects and samples excluded from the analysis will be clearly documented in the PK report.

Descriptive statistics will be used to summarize venetoclax concentrations at each sampling time point and PK parameters (including, but not limited to: C_{max} , T_{max} , and AUC) at each dosing interval.

Individual and mean plasma venetoclax concentration time profiles will be plotted.

Venetoclax data from this study may also be combined with data from other studies performed with ibrutinib in subjects with hematologic malignancies as part of a population-PK analysis using nonlinear mixed effects models. For the population-PK analysis, covariates that could potentially correlate with plasma PK parameters will be evaluated. The results of the population-PK analyses (if performed) will be presented in a separate report.

Venetoclax model-derived exposure parameters (PK parameters) may be used to explore PK/PD correlation between the exposure of venetoclax with relevant clinical [REDACTED] information to assess effectiveness and toxicity.

10.6. [REDACTED]

[REDACTED]
[REDACTED] Descriptive statistics will be used to summarize these exploratory endpoints. The detail will be given in SAP. Results will be presented in a separate report.

10.7. Data Review Committee (DRC)

A DRC will be established to monitor data in the MRD Cohort Safety Run-in Period (defined as the date of first dose of ibrutinib at Cycle 1 Day 1 through the DLT evaluation period) to ensure the safety of the subjects enrolled in this novel combination study. The committee will meet periodically to review safety data. After the review of the first 6 evaluable subjects who have completed the combination of ibrutinib + dose ramp-up of venetoclax with an additional week of follow up, the DRC may make recommendations regarding the recommended doses and continuation of the study. A follow-up DRC review will occur after all subjects in the Safety Run-in Period have either discontinued therapy and/or have completed the venetoclax dose ramp up and 1 week follow up, then the DRC may make additional recommendations regarding the recommended doses.

The DRC will consist of the Medical Monitor or designee, a Drug Safety representative, a biostatistician, and at least 2 participating Investigators.

11. ADVERSE EVENT REPORTING

Timely, accurate, and complete reporting and analysis of safety information from clinical studies are crucial for the protection of subjects, investigators, and the Sponsor, and are mandated by regulatory agencies worldwide. The Sponsor has established Standard Operating Procedures in conformity with regulatory requirements worldwide to ensure appropriate reporting of safety information; all clinical studies conducted by the Sponsor or its affiliates will be conducted in accordance with those procedures.

11.1. Definitions

11.1.1. Adverse Events

An AE is any untoward medical occurrence in a subject administered a pharmaceutical product and which does not necessarily have a causal relationship with this treatment. An AE can therefore be any unfavorable and unintended sign (including a clinically significant abnormal laboratory finding, for example), symptom, or disease temporally associated with the use of an investigational study drug, whether or not considered related to the study drug ([ICH-E2A, 1995](#)).

For the purposes of this clinical study, AEs include events which are either new or represent detectable exacerbations of pre-existing conditions.

The term "disease progression" should not be reported as an AE term. As an example, "worsening of CLL/SLL" or the clinical diagnosis that is associated with disease progression should be reported.

Adverse events may include, but are not limited to:

- Subjective or objective symptoms provided by the subject and/or observed by the investigator or study staff including laboratory abnormalities of clinical significance.
- Any AEs experienced by the subject through the completion of final study procedures.
- AEs not previously observed in the subject that emerge during the protocol-specified AE reporting period, including signs or symptoms associated with the underlying disease that were not present before the AE reporting period
- Complications that occur as a result of protocol-mandated interventions (eg, invasive procedures such as biopsies).

The following are NOT considered AEs:

- **Pre-Existing Condition:** A pre-existing condition (documented on the medical history CRF) is not considered an AE unless the severity, frequency, or character of the event worsens during the study period.

- **Pre-Planned or Elective Hospitalization:** A hospitalization planned before signing the ICF is not considered an SAE, but rather a therapeutic intervention. However, if during the pre-planned hospitalization an event occurs, which prolongs the hospitalization or meets any other SAE criteria, the event will be considered an SAE. Surgeries or interventions that were under consideration, but not performed before enrollment in the study, will not be considered serious if they are performed after enrollment in the study for a condition that has not changed from its baseline level. Hospitalization required per protocol for subjects at high risk for TLS (high tumor burden, or those with CrCl <80 mL/min) are not considered AEs unless the hospitalization is prolonged >24 hours or if additional intervention, not described as mandatory prophylaxis in [Table 4](#), is required. Elective hospitalizations for social reasons, solely for the administration of therapy, or due to long travel distances are also not SAEs.
- **Diagnostic Testing and Procedures:** Testing and procedures should not to be reported as AEs or SAEs, but rather the cause for the test or procedure should be reported.
- **Asymptomatic Treatment Related Lymphocytosis:** This event should also not be considered an AE. Subjects with treatment-related lymphocytosis should remain on study treatment and continue with all study-related procedures.

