Safety Run-in Period will be instituted to evaluate safety and tolerability of the combination, and determination of the recommended doses. Additionally, venetoclax will be introduced after 3 cycles (1 cycle = 28 days) of single-agent ibrutinib lead-in, representing the period after the ibrutinib-induced lymphocytosis peak and where most treated subjects will have experienced significant reduction in lymphadenopathy. Utilizing the previously published calculations to determine TLS risk categories for venetoclax based on tumor burden ([Seymour 2014](#), [Appendix H](#) as noted in the [VENCLEXTA® \(venetoclax\) prescribing information](#), TLS risk at baseline and at first assessment were calculated utilizing CT scans after 4 cycles of ibrutinib from the RESONATE-2 ibrutinib treatment naïve Phase 3 CLL study (N=135) and after 2 cycles of ibrutinib in PCYC-1102 Phase 1b/2 treatment naïve cohorts (N=27). The percent of subjects at high or moderate-risk for tumor lysis syndrome (TLS) at baseline was reduced from 81% to 59% after 2-4 cycles of ibrutinib, and the percent of subjects at high-risk for TLS at baseline was reduced from 28% to 7% after 2-4 cycles of ibrutinib. Due to transient increase in ALC, a minority (5%) of patients increased from low to medium risk at first assessment, however no patients increased from low or medium to high risk. For patients with treatment-naïve CLL or SLL with CrCl <80 mL/min, 36% (25/69) with medium TLS risk at baseline were reduced to low risk by first assessment and 26% (10/30) with high TLS risk at baseline were reduced to low risk by first assessment, further reducing the overall percent of patients requiring hospitalization ([Wierda 2017](#)). Therefore, employing a 3-cycle ibrutinib lead-in and sequencing ibrutinib prior to venetoclax should provide tumor debulking and convert higher TLS risk subjects to lower TLS risk subjects.

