5.4.2.2. Prophylaxis and Management of Tumor Lysis Syndrome

Venetoclax can cause rapid reduction in tumor and thus poses a risk for TLS in the initial 5-week ramp-up phase. Changes in electrolytes consistent with TLS that require prompt management can occur as early as 6-8 hours following the first dose of venetoclax and at each dose increase. The risk of TLS is a continuum based on multiple factors, including tumor burden and comorbidities. Subjects with high tumor burden are a greater risk of TLS when initiating venetoclax. Reduced renal function further increases the risk. The risk may decrease as tumor burden decreases with venetoclax treatment.

Subjects at high risk of TLS (at least one lesion ≥ 10 cm; or at least one lesion ≥ 5 cm plus circulating lymphocytes $>25,000$ cells/ μ L) will be hospitalized during the first 24-48 hours of treatment for TLS monitoring and hydration. Hospitalization should be considered for subjects with medium risk of TLS and baseline creatinine clearance <80 mL/min. Hospitalization for subjects lacking immediate access to a facility capable of correcting TLS promptly or for subjects who are otherwise considered at risk for TLS is allowed at the discretion of the investigator.

In all subjects, perform tumor burden assessments, including radiographic evaluation (eg, CT scan), assess blood chemistry (potassium, uric acid, phosphorus, calcium, and creatinine) and correct pre-existing abnormalities prior to initiation of treatment with venetoclax in Cycle 4.

In all subjects, assess patient-specific factors for level of risk of TLS and provide prophylactic hydration and anti-hyperuricemics to subjects prior to first dose of venetoclax to reduce risk of TLS. Employ more intensive measures (intravenous hydration, frequent monitoring, and hospitalization) as overall risk increases.

Table 4. TLS Prophylaxis Based on Tumor Burden from Clinical Trial Data (consider all co-morbidities before final determination of prophylaxis and monitoring schedule)

Tumor Burden		Prophylaxis		Blood Chemistry Monitoring ^{c,d}
		Hydration ^a	Anti-hyperuricemics	Setting and Frequency of Assessments
Low	All LN <5 cm AND ALC <25 x10 ⁹ /L	Oral (1.5-2 L)	Allopurinol ^b	Outpatient 
 Pre-dose, 6 to 8 hours, 24 hours at first dose of 20 mg and 50 mg Pre-dose at subsequent ramp-up doses

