Medium	Any LN 5 cm to <10 cm OR ALC ≥25 x10 ⁹ /L	Oral (1.5-2 L) and consider additional intravenous	Allopurinol ^b	Outpatient 
 Pre-dose, 6 to 8 hours, 24 hours at first dose of 20 mg and 50 mg Pre-dose at subsequent ramp-up doses Consider hospitalization for subjects with CrCl <80mL/min at first dose of 20 mg and 50 mg; see below for monitoring in hospital
High	Any LN ≥10 cm OR ALC ≥25 x10 ⁹ /L AND any LN ≥5 cm	Oral (1.5-2 L) and intravenous (150-200 mL/hr as tolerated)	Allopurinol ^b ; consider rasburicase if baseline uric acid is elevated	In hospital at first dose of 20 mg and 50 mg 
 Pre-dose, 4, 8, 12 and 24 hours Outpatient at subsequent ramp-up doses 
 Pre-dose, 6 to 8, and 24 hours

ALC = absolute lymphocyte count; LN = lymph node

- Administer intravenous hydration for any patient who cannot tolerate oral hydration.
- Start allopurinol or xanthine oxidase inhibitor 2 to 3 days prior to initiation of venetoclax.
- Evaluate blood chemistries (potassium, uric acid, phosphorus, calcium, and creatinine); review in real time.
- For subjects at risk of TLS, monitor blood chemistries at 6 to 8 hours and at 24 hours at each subsequent ramp-up dose. A ±30-minute window is acceptable for the 4 and 8 hr chemistry assessments, a ±1 hr window is acceptable for the 12-hour chemistry assessments, and a ±2-hour window is acceptable for the 24-hour chemistry assessments.
- Hematology and Serum Chemistry may be collected up to 24 hours prior to each venetoclax ramp-up (Cycle 4 Weeks 2-4 and Cycle 5 Week 1), to allow for flexibility in start of ramp-up dose. Hematology and serum chemistry can be drawn on day of dosing to allow for comparisons, but results are not required before dosing decision is made

Hydration: Ensure adequate hydration prior to initiating therapy with venetoclax and throughout the ramp-up phase, especially the first day of each ramp-up dose. Administer intravenous (IV) fluids as indicated based on overall risk of TLS or for those who cannot maintain adequate oral hydration.

Anti-hyperuricemic agents: Administer uric acid reducing agents (eg, allopurinol).

Start 2-3 days prior to initiation of venetoclax; consider continuing through the ramp-up phase.

Laboratory Assessments:

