Pre-dose: Assess blood chemistries (specifically creatinine, uric acid, potassium, phosphorus, and calcium) prior to initiating venetoclax to evaluate kidney function and correct pre-existing hyperuricemia, hyperkalemia, hyperphosphatemia, or hypocalcemia to normal levels before

administering venetoclax. Reassess blood chemistries before starting each subsequent ramp-up dose of venetoclax.

Post-dose: For subjects at low or medium risk of TLS, monitor blood chemistries at 6-8 hours and at 24 hours after initiating venetoclax at the 20 mg and 50 mg doses. For subjects at high risk of TLS, monitor blood chemistries in the hospital at 4, 8, 12, and 24 hours after initiating venetoclax at the 20 mg and 50 mg doses; subsequent ramp-up doses can be administered in the outpatient setting with monitoring of blood chemistries at 6-8 hours and at 24 hours after initiating venetoclax. Electrolyte abnormalities should be corrected promptly. The next dose of venetoclax should not be administered until the 24-hour blood chemistry results have been evaluated and hyperuricemia, hyperkalemia, hyperphosphatemia, or hypocalcemia are corrected to normal levels.

Hospitalization: Based on investigator assessment of TLS risk, subjects at high risk of TLS require hospitalization on the day of the first dose of venetoclax 20 mg and 50 mg doses for more intensive prophylaxis and monitoring through the first 24 hours. Subsequent ramp-up doses can be administered on an outpatient basis; however, hospitalization may be considered based on reassessment of risk. See [Appendix H](#) for TLS Risk Categories and [Appendix J](#) for Recommendations for Initial Management of Electrolyte Abnormalities and Prevention of Tumor Lysis.

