11.1.2. Serious Adverse Events

A serious adverse event (SAE) based on International Conference on Harmonisation (ICH) and EU Guidelines on Pharmacovigilance for Medicinal Products for Human Use is any untoward medical occurrence that at any dose:

- Results in death (ie, the AE actually causes or leads to death).
- Is life-threatening. Life-threatening is defined as an AE in which the subject was at risk of death at the time of the event. It does not refer to an event which hypothetically might have caused death if it were more severe. If either the investigator or the Sponsor believes that an AE meets the definition of life-threatening, it will be considered life-threatening.
- Requires unplanned in-patient hospitalization >24 hours or prolongation of existing hospitalization.
- Results in persistent or significant disability/incapacity (ie, the AE results in substantial disruption of the subject's ability to conduct normal life functions).
- Is a congenital anomaly/birth defect.
- Is an important medical event that may not result in death, be immediately life-threatening or require hospitalization, but may be considered an SAE when, based upon appropriate medical judgment, the event may jeopardize the subject or subject may require intervention to prevent one of the other outcomes listed in this definition. Examples of such events are intensive treatment in an emergency department or at home for allergic bronchospasm, blood dyscrasias, or convulsion that does not result in hospitalization; or development of drug dependency or drug abuse.

Given that the investigator's perspective may be informed by having actually observed the event, and the Sponsor is likely to have broader knowledge of the drug and its effects to inform its

evaluation of the significance of the event, if either the Sponsor or the investigator believes that the event is serious, the event will be considered serious.

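### The AE exemption for TLS admissions stops at a 24-hour limit with no stated starting point, while the required stay is given in two ways, so event-free admissions may be coded differently by site

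*Protocol*

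**What the plan says.** Protocol Section 11.1.1, under pre-planned or elective hospitalization, covers "Hospitalization required per protocol for subjects at high risk for TLS (high tumor burden, or those with CrCl <80 mL/min" and states that these admissions "are not considered AEs unless the hospitalization is prolonged >24 hours", or unless an intervention beyond the mandatory prophylaxis in Table 4 is needed.

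Section 5.4.2.2 describes the stay itself. Its opening text says that high-risk subjects "will be hospitalized during the first 24-48 hours of treatment for TLS monitoring and hydration". Its later paragraph on hospitalization requires admission on the day of the first 20 mg and 50 mg doses "for more intensive prophylaxis and monitoring through the first 24 hours". Table 4 places high-risk subjects "In hospital at first dose of 20 mg and 50 mg", with chemistries from pre-dose to 24 hours and a window of 2 hours either side of the 24-hour draw. For medium-risk subjects with creatinine clearance below 80 mL/min, Section 5.4.2.2 and Table 4 ask only that admission be considered.

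Section 11.1.2 lists as a seriousness criterion: "Requires unplanned in-patient hospitalization >24 hours or prolongation of existing hospitalization".

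**The concern.** The exemption exists so that admissions ordered by the protocol do not enter the safety data as adverse events. Its limit is a clock figure that coincides with the shorter stated stay and lies at the bottom of the longer one. A site that follows the longer wording could keep a subject past 24 hours with nothing wrong and then not know whether the exemption still applies.

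What is at stake is consistent adverse-event coding of prophylactic admissions around venetoclax ramp-up. SAP Section 5 and its Table 3 summarize treatment-emergent and serious events as recorded. The rule also stays in use later, because venetoclax reintroduction repeats the ramp-up and TLS prophylaxis (Protocol Section 8.4, Appendices D and E).

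**Working it through.** The plan gives no figure to reproduce. The check sets the passages side by side, with simple arithmetic on hours.

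1. **Limit.** Section 11.1.1: 24 hours, origin not stated.

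2. **Required stay, longer wording.** Opening text of Section 5.4.2.2: 24 to 48 hours. Excess over the limit: 24 − 24 = 0 hours, up to 48 − 24 = 24 hours. This wording refers to the start of treatment and does not mention the 50 mg step.

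3. **Required stay, shorter wording.** The hospitalization paragraph runs to 24 hours after dosing. Under Table 4 the last draw falls at 24 − 2 = 22 to 24 + 2 = 26 hours after the dose. Stay = (admission to dose) + (dose to last draw) + (last draw to discharge).
   - Draw at 22 hours: the stay remains within 24 hours if the first and third terms total no more than 24 − 22 = 2 hours.
   - Draw at 26 hours: the stay exceeds 24 hours by at least 26 − 24 = 2 hours.

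   So even the shorter wording allows a compliant stay on either side of the limit.

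4. **Two readings of *prolonged*.**
   - Total stay above 24 hours: an event-free stay under step 2, or at the late end of step 3, falls outside the exemption.
   - More than 24 hours beyond the required stay: no conflict arises, but the reference is 24 hours in one paragraph and 24-48 hours in another.

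5. **Who is covered.** Section 11.1.1 places creatinine clearance below 80 mL/min within the group whose admission the protocol requires. Section 5.4.2.2 and Table 4 make it a consideration, for medium-risk subjects only.

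6. **Rough scale.** Section 1.4 reports, from earlier ibrutinib studies, that "the percent of subjects at high-risk for TLS at baseline was reduced from 28% to 7% after 2-4 cycles of ibrutinib". Assuming that 7% applies to the 150 + 125 = 275 planned subjects: 0.07 × 275 = 19.25, about 19 subjects. With two admissions each (20 mg and 50 mg): 19.25 × 2 = 38.5, about 38 admissions. Medium-risk subjects who are admitted are not counted.

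**The case against.** The strongest reply is that *prolonged* naturally means extended beyond what was planned. The same bullet uses the verb that way when it deals with an event that lengthens a pre-planned stay, and on that reading nothing collides. The reading is available, but the text does not settle it. The rule for pre-planned stays is tied to an event, whereas the TLS sentence gives a bare hour limit with no event condition, and Section 11.1.2 uses the same figure for the length of a stay. Even on the favorable reading, sites need one reference stay and have two.

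Several further points against the concern stand:

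- A reader might infer that compliant stays almost always pass 24 hours. The documents do not support that. The last draw may be taken at 22 hours. Pre-dose laboratory tests may be collected up to 24 hours ahead for the 50 mg step (Table 4 notes), and for both steps in the Fixed Duration cohort (Appendix B). The 24-hour result must be evaluated before the next dose, not before discharge.
- Losing the exemption does not create an adverse event. Section 11.1.1 still requires an untoward medical occurrence.
- A reader might infer that these stays become serious adverse events. Section 11.1.2 requires an untoward occurrence with an unplanned stay or a prolongation, and a scheduled event-free admission is neither. The remaining risk is only that *prolonged* in Section 11.1.1 is read as the prolongation criterion in Section 11.1.2.

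**Conclusion.** The concern holds as an internal contradiction in safety-reporting rules. Section 11.1.1 sets a limit without an origin, Section 5.4.2.2 gives the required stay two lengths, and the sections disagree on whether admission for reduced creatinine clearance is required or only considered. The result is that identical prophylactic admissions may be coded differently across sites.

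The scale of about 19 subjects and 38 admissions rests on carrying the 7% over from earlier studies to this trial's planned enrollment. It shows how many admissions the wording could touch. It does not count spurious records, and it cannot be turned into a rise in the serious adverse event rate. That would need every such stay to pass 24 hours, every site to apply the strict reading, and every stay to be classed as serious in a subject with no other serious event.

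A reader might also suspect that the TLS endpoint is contaminated. It is not: TLS risk reduction is defined by tumor-burden category (Protocol Section 10.4.8), and its supportive analysis in SAP Table 2 counts hospitalization indicated by risk, not adverse-event records. Dose-limiting toxicities (Section 5.2.1) are clinical TLS or graded toxicities, not admissions. The primary endpoints, power and error rates are untouched.

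**What to change.** Reconcile the opening text of Section 5.4.2.2, its hospitalization paragraph, Table 4 and Section 11.1.1, so that they give one reference stay and one statement of whose admission the exemption covers. This review takes no position on how long the stay should be or who should be admitted.

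Then reword Section 11.1.1 so that a TLS prophylaxis admission loses the exemption only if it extends beyond the stay specified in Section 5.4.2.2 because of an untoward event, or needs an intervention not listed in Table 4.

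The cost is one sentence in Section 11.1.1 and the reconciliation of the stay and eligibility wording elsewhere. The downside is a slightly narrower adverse-event trigger; untoward events during the stay remain reportable.
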